#### **B.6.9. Test Arm: 1 Month After Device Activation ( $\pm$ 15 days)**

Subjects will visit the study site where they will be assessed for pain intensity. Programming adjustments may be made, as needed. As per standard practice, anterior-posterior (AP) and lateral X-ray imaging may be done if significant lead migration is suspected. Subjects will be assessed for adverse events, healthcare utilization and medication usage.

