#### **B.6.14. Test Arm: 18 Months After Device Activation ( $\pm 45$ days)**

Subjects will visit the study site where they will be assessed for pain, [REDACTED]

[REDACTED] Programming adjustments may be made, as needed. As per standard practice, anterior-posterior (AP) and lateral X-ray imaging may be done if significant lead migration is suspected. Subjects will also be assessed for possible adverse events, healthcare utilization, and medication usage.

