### **B.6.16 Control Arm: CMM**

The choice of appropriate Conventional Medical Management will be made **by the Investigator as determined to be the best standard of care** for each individual subject i.e. optimized individual conventional therapy. These treatments would be generally consistent with the American College of Physicians and the American Pain Society Guidelines as published in the Annals of Internal Medicine (<http://annals.org/article.aspx?articleid=736814>) and European/UK guidelines. The CMM treatment can be modified at any moment by the investigators based on their clinical evaluation and local standard of care. They may also consist of one or more of the following treatments:

- Medications: Over-the-counter Analgesic medications, opioid medications, Nonsteroidal anti-inflammatory drugs (NSAIDs), Anticonvulsants, Antidepressants, topical analgesics
- Combined physical and psychological management (CPPM)
- Physical therapy
- Back rehabilitation program
- Spinal manipulation and spinal mobilization
- Traction
- Acupuncture
- Cognitive behavioral therapy (CBT)
- Biofeedback
- Nerve blocks
- Radio frequency ablation
- Epidural steroid injections
- Transcutaneous electrical nerve stimulation (TENS)
- Intradiscal electrothermal therapy (IDET)
- Nucleoplasty, also called plasma disc decompression (PDD) or similar

Subjects will continue under CMM therapy until the 24 month visit. No interventions (e.g., facet joint blocks) shall be performed during the 4 weeks leading up to a follow-up visit.

Note: except for the 1 month follow-up visit this is not applicable as the time interval between Randomization and 1 month visit may be too short due to organizational inconvenience. We recommend however to complete the CMM intervention after the Randomization or short after the Randomization and make use of the available time windows at the 1 month visit (i.e. 15 days) to make sure this intervention can be completed within the proposed time window.

---

 Clinical guidelines for the management of low back pain in primary care: an international comparison; Spine. 26(22):2504-2513, November 15th, 2001. Koes et al

 Clinical guidelines for the management of non-specific low back pain in primary care: an updated overview; European Spine Journal 27, 2791-2803(2018). Oliveira et al

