 Low back pain and sciatica in over 16s: assessment and management. NICE guideline. Published 30 November 2016. [www.nice.org.uk/guidance/ng59](http://www.nice.org.uk/guidance/ng59)

**At the 1 month ( $\pm 15$  days)** follow up visit, subjects will be assessed for pain and for adverse events, medication usage, healthcare utilization and treatment usage.

**At the 3 month ( $\pm 21$  days)** follow up, subjects will visit the study site where they will be assessed for pain, [REDACTED]

[REDACTED] Subjects will also be assessed for possible adverse events, medication usage, healthcare utilization and treatment usage.

**At the 6 month ( $\pm 31$  days)** follow up visit, subjects will visit the study site where they will be assessed for pain, [REDACTED]

[REDACTED] Subjects will also be assessed for possible adverse events, medication usage, healthcare utilization, [REDACTED] and treatment usage. Subjects will have the option to crossover to the test treatment arm if the subject is not receiving sufficient pain relief from CMM alone and desires to try the other treatment arm. They will be indicated as 'crossover to DTMTM SCS'. See Section B.6.1 – Crossover.

Those subjects that switch to the test arm will be considered a failure in the control arm. Subjects that crossover to the test arm will follow the steps described in Sections B.6.5. to B.6.13, and the subjects will be followed for another 12 month which includes 1, 3, 6, 9 and 12 months visits post-device activation.

For those subjects that decide to crossover to the DTMTM SCS + CMM arm, there will be no additional scheduled follow-up visits in the study beyond the 12 month post-device activation visit. Following the last scheduled study visit, subjects will be followed by the Investigator at regular intervals, as dictated by standard of care at each site, in order to facilitate pain management, stimulation adjustments, possible revisions and/or replacements of neurostimulation components. Any additional non-study related monitoring of the subject will be the responsibility of the subject's personal physician, as dictated by reasonable medical care.

Subjects that continue with CMM and do not cross over, will visit the study site at the **9 month ( $\pm 31$  days), 12 month ( $\pm 31$  days), and 18 month ( $\pm 31$  days)** post-randomization for follow up visits, where they will be assessed for pain, [REDACTED]

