#### **B.6.18. Telephone Calls**

Subjects will be contacted by the study coordinator, via a telephone call, before each study visit. The study coordinator will check on the well-being of the subject, remind the subject of the upcoming scheduled visit, remind the subject not to change pain medication usage prior to the scheduled visit, and remind the subject to contact the Investigator/study staff should he/she have any concerns or questions. The study site may also call the subject periodically to answer subject questions and to check on their health. Participants may also be contacted by a representative of SGX to see if they are having problems with the equipment and answer questions related to the use of the device. The telephone calls should be made two to three weeks *before* every scheduled visit.

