#### **B.6.19. Other Assessments and Information**

At any time during the study, for those subjects implanted with SCS, if lead migration is suspected, the subject may have additional AP and lateral X-rays taken to confirm the new lead position in order to aid the Investigator in determining a course of action.

As per the Intellis™ neurostimulator's instructions for use:

- Paresthesia testing may also be performed to assess lead location and therapy coverage of pain areas.
- Programming adjustments may be made based on patient feedback following assessment.

Additional information on Medication Usage when allocated to the DTM™ SCS arm and crossover subjects (from CMM to DTM™ SCS):

- It is recommended that the investigator instructs all subjects to take the Baseline doses of pain medication until the 6 month visit. However, after Device Activation Visit, the Investigator may reduce the dose of pain medication if the subject is benefitting greatly from SCS and not benefitting from Baseline dose pain medication.
  - Subjects should not fluctuate medication usage nor dosages even if the dose is at or below Baseline. The investigator will instruct all subjects to maintain stable dosing of medication for at least two weeks prior to scheduled follow-up visits.
- For the trial and permanent implants, the clinical site's standard practice for prophylactic pre-surgery antibiotics and post-surgery pain medications will be

followed. Investigators will instruct subjects not to change usage of any other concomitant pain medications.

Additional information on Medication Usage when allocated to the CMM arm and crossover subjects (from DTM™ SCS to CMM):

- Subjects should follow the investigator's instructions. The investigator will instruct all subjects to maintain stable dosing of medication for at least two weeks prior to scheduled follow-up visits.

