**Table 1a - Schedule of Study Activities for the Test arm (DTMTM SCS)**

Assessment	Pre-Trial		Trial Phase		Permanent Implant Phase						
	Baseline	Enrollment /Entry Criteria	End of Trial (EoT)	Trial Implant	0-30 d from Trial Implant	0-90 d from EoT	0-14 d from Perm Implant	2-3 Weeks before 12 Month Visit	2-3 Weeks before 9 Month Visit	2-3 Weeks before 6 Month Visit	2-3 Weeks before 3 Month Visit
Window Visit	Might be combined into one visit, if all enrollment and entry criteria are fulfilled at time of baseline assessment										
Informed Consent*	X		X	X							
Medication Usage	X	X									
Pain Intensity (VAS)	X			X							
Eligibility criteria	X										
Pregnancy Test	[X]			[X]							
Medical/Surgical History	X										
AP/Lateral X-Rays	[REDACTED]		X	X	X		[X]	[X]	X	X	X
Healthcare Utilization			X						X	X	[X]
Adverse Event Monitoring			X	X	X	X	X	X	X	[X]	[X]
Device Programming §				X				X	[X]	[X]	
Cross over									[X]	[X]	
Study Completion				[X]	[X]	[X]	[X]	[X]	[X]	[X]	X

[X] Optional activity.

\*For subjects consented prior to the EC approval of the revised consent, they may be reconsented at any study visit.

§As per the IntellisTM neurostimulator instructions for use. This may also include paresthesia testing.

Unscheduled visit: VAS, Adverse Event monitoring and medication to be collected

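### The 4-week ban on interventions before a follow-up visit is written for the control arm only, and the visible text names treatment usage only at control visits

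*Protocol*

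**What the plan says.** **Treatment.** Protocol B.4 gives CMM to both arms: alone in control, and alongside stimulation in test. The menu in B.4 and B.6.16 has 15 entries. Five are procedures: nerve blocks, radio frequency ablation, epidural steroid injections, intradiscal electrothermal therapy and nucleoplasty. On changes, the control text says: "The CMM treatment can be modified at any moment by the investigators based on their clinical evaluation and local standard of care".

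**Assessment.** B.5.4 says that neither subjects nor site staff are blinded. The primary endpoint rests on a back pain VAS that the subject scores (B.7.3, B.8.1).

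**Timing of interventions.** B.6.16, headed as the control arm section, says: "No interventions (e.g., facet joint blocks) shall be performed during the 4 weeks leading up to a follow-up visit". A note waives this before the 1-month visit, because the time since randomization may be too short.

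**Timing of drugs.** B.6.19 has one block for the stimulation arm and one for the CMM arm. Both contain: "The investigator will instruct all subjects to maintain stable dosing of medication for at least two weeks prior to scheduled follow-up visits". The call before each visit (B.6.18) is to "remind the subject not to change pain medication usage prior to the scheduled visit", without distinction of arm.

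**Recording.** At the control 1-month visit "subjects will be assessed for pain and for adverse events, medication usage, healthcare utilization and treatment usage". The test 1-month visit (B.6.9) reads: "Subjects will be assessed for adverse events, healthcare utilization and medication usage". At 18 months (B.6.14) the closing sentence of the test section reads: "Subjects will also be assessed for possible adverse events, healthcare utilization, and medication usage". B.6.1 says that control subjects have the same assessments as test subjects at all follow-up visits.

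**Reporting.** SAP sections 5.4 to 5.11 cover disposition, baseline, efficacy, poolability, safety, interim looks and deviations. None names a table of treatment received.

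**The concern.** The comparison is stimulation plus CMM against CMM alone. Some divergence in CMM after allocation belongs to the strategy; B.6.19, for instance, allows lower drug doses when stimulation works well. A difference in what is permitted just before the endpoint is another matter. A block or injection given shortly before the 6-month VAS can lower that score for reasons unrelated to stimulation. If one arm is barred from it and the other is not, the responder comparison is exposed to an influence that one sentence would remove.

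If non-drug treatment is also recorded less fully in the test arm, and no table sets CMM side by side, a reader of the final report could not tell whether this happened.

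**Working it through.** **1. The plan's own figure.** Inputs from Protocol B.5.5.1: 60% and 30% responders, 50 per arm, two-sided alpha 0.05, Pearson chi-square.

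Power = Φ[(|p1 − p2|·√n − 1.96·√(2p̄(1 − p̄))) / √(p1(1 − p1) + p2(1 − p2))], with p̄ = 0.45

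- 0.30·√50 = 2.121
- 1.96·√0.495 = 1.379
- √(0.24 + 0.21) = 0.671
- (2.121 − 1.379) / 0.671 = 1.107, and Φ(1.107) = 0.866

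Exact enumeration gives 0.876. Both agree with the stated power above 85%, and nothing below changes it.

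**2. Timing rules by arm.**

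| Rule before a follow-up visit | Control | Test |
|---|---|---|
| Stable drug dosing, 2 weeks | Stated, B.6.19 | Stated, B.6.19 |
| Reminder call on pain medication | Stated, B.6.18 | Stated, B.6.18 |
| No interventions, 4 weeks | Stated, B.6.16 | Not stated in B.6.5 to B.6.15, B.6.19 or the SAP |

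Where the plan wants a pre-visit dosing rule in both arms, it writes it twice. The intervention rule appears once. Its waiver is argued from the interval since randomization, which is the control arm's clock; test visits are timed from Device Activation (B.5.5). Read literally, an injection three weeks before the 6-month visit is a deviation in control and not in test, so the deviation summary in SAP 5.11 would not reveal it in test.

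**3. Recording by arm, visible text only.**

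| Visit | Control (B.6.16) | Test |
|---|---|---|
| 1 month | Treatment usage listed | Not listed; B.6.9 has no redaction |
| 3, 9, 18 months | Listed | Not in the closing sentence; an earlier sentence is redacted (B.6.10, B.6.12, B.6.14) |
| 6, 12, 24 months | Listed | Closing list itself has a redaction (B.6.11, B.6.13, B.6.15) |

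The control text names treatment usage in addition to medication usage and healthcare utilization, so the plan treats the three as separate items. The legible rows of Table 1a show no such row. Its footnote, "Unscheduled visit: VAS, Adverse Event monitoring and medication to be collected", does not establish a difference between arms, because the body of Table 1b cannot be read. B.6.1 promises the same assessments in both arms, but its own list does not name treatment usage either.

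**4. Length of the counting window.** Test month 6 counts from Device Activation. The listed maxima are 30 days of trial (B.6.5), 90 days to implant (B.6.7) and 14 days to activation (B.6.8):

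30 + 90 + 14 = 134 days

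Any wait between randomization and the trial implant comes on top. With six months taken as 183 days, (183 + 134) / 183 = 1.73. With the same CMM rate in both arms, a raw count from randomization to the 6-month visit could therefore be about 1.7 times as high in test.

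**5. Scale.** The documents give no CMM difference, so the shifts here are assumptions (exact two-sided chi-square, 50 per arm).

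- Both arms truly at 30%, with unequal CMM lifting test by 5 or 10 points: rejection rises from 5.0% to 8.2% or 18.0%.
- 60% against 30%, with control lifted by 5 or 10 points: power falls from 87.6% to 73.4% or 54.3%.

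These figures hold for a shift from any cause. They neither measure this gap nor show that a shift exists.

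**The case against.** **B.6.16 may define CMM for everyone.** Test subjects receive CMM too, and the ban refers to a follow-up visit without naming an arm. The freedom to change CMM is likewise written only in control text, so it would be inconsistent to read the freedom as general and the ban as control-only. This is a fair reading, and it may be what was intended. It does not settle the matter: the section is headed as the control arm, no test section refers to it, and the waiver fits only the control clock. Sites could read it either way, which is reason enough to state it.

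**The recording gap may not exist.** B.6.1 promises equal assessments. Healthcare utilization is listed at every test follow-up visit and may well capture blocks and injections. Exceptional remote visits also ask about concurrent procedures (B.9.1). No form is visible. This stands: a reader might infer that CMM in the test arm goes unrecorded, and the documents do not support that. What can be shown is an inconsistency between B.6.1 and the visit lists.

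**Drug against non-drug.** A reader might infer that drug differences will be visible and only non-drug differences hidden. The SAP does not bear this out, since it names no medication table either. The drug rules differ by arm as well: B.6.19 recommends Baseline doses to month 6 in test and leaves control to the investigator.

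**Recording intended CMM before allocation.** This could be asked for, but it would be a preference. It would not bind later care, and the Baseline section is partly redacted.

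**Conclusion.** The point holds as a gap in wording and reporting that is cheap to close. Its firm part is the 4-week rule, which on the visible text is stated for control only, in an open-label trial with a self-reported endpoint. The recording part is weaker: treatment usage is named only at control visits in what can be read, and a test-arm item cannot be ruled out. The absence of a CMM table from the SAP does not depend on redacted text.

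A reader might go on to infer that the trial is biased towards the device. The documents do not support that. A late block in a test subject would favour test; freer adjustment of drugs in control would favour control; and nothing says how often either would occur. Size and direction are unknown, and the stated sample size and power stand.

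**What to change.** 1. **Protocol B.6.19:** state in both medication-usage blocks, which already name crossover subjects, that no CMM intervention is given in the 4 weeks before a follow-up visit. Keep the 1-month waiver for control only, since its reason is the short time from randomization. Word the rule so that implantation, lead revision and programming are not caught.
2. **Protocol B.6.9 to B.6.15 and Table 1a:** list the same treatment-usage item as at control visits, in line with B.6.1. If the form already exists, this is only a clarification.
3. **SAP:** add one descriptive table by arm of CMM received, split into drug, non-drug and interventional. Report it per subject-month or over a common window, because raw counts from randomization would cover unequal time. Show interventions in the 4 weeks before the 6-month VAS separately.

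The cost is one rule stated for both arms, one form item at test visits and one table, with no extra visits or subjects. The drawback is that some test subjects may wait for a block.

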#### **B.6.17. Unscheduled Visits**

Unscheduled visits may occur at any time during the study for the assessment of possible adverse events, changes in pain medication, and therapy adjustments. Each unscheduled visit will be documented and recorded on an eCRF.

#### **B.6.18. Telephone Calls**

Subjects will be contacted by the study coordinator, via a telephone call, before each study visit. The study coordinator will check on the well-being of the subject, remind the subject of the upcoming scheduled visit, remind the subject not to change pain medication usage prior to the scheduled visit, and remind the subject to contact the Investigator/study staff should he/she have any concerns or questions. The study site may also call the subject periodically to answer subject questions and to check on their health. Participants may also be contacted by a representative of SGX to see if they are having problems with the equipment and answer questions related to the use of the device. The telephone calls should be made two to three weeks *before* every scheduled visit.

#### **B.6.19. Other Assessments and Information**

At any time during the study, for those subjects implanted with SCS, if lead migration is suspected, the subject may have additional AP and lateral X-rays taken to confirm the new lead position in order to aid the Investigator in determining a course of action.

As per the Intellis™ neurostimulator's instructions for use:

- Paresthesia testing may also be performed to assess lead location and therapy coverage of pain areas.
- Programming adjustments may be made based on patient feedback following assessment.

Additional information on Medication Usage when allocated to the DTM™ SCS arm and crossover subjects (from CMM to DTM™ SCS):

- It is recommended that the investigator instructs all subjects to take the Baseline doses of pain medication until the 6 month visit. However, after Device Activation Visit, the Investigator may reduce the dose of pain medication if the subject is benefitting greatly from SCS and not benefitting from Baseline dose pain medication.
  - Subjects should not fluctuate medication usage nor dosages even if the dose is at or below Baseline. The investigator will instruct all subjects to maintain stable dosing of medication for at least two weeks prior to scheduled follow-up visits.
- For the trial and permanent implants, the clinical site's standard practice for prophylactic pre-surgery antibiotics and post-surgery pain medications will be

followed. Investigators will instruct subjects not to change usage of any other concomitant pain medications.

Additional information on Medication Usage when allocated to the CMM arm and crossover subjects (from DTM™ SCS to CMM):

- Subjects should follow the investigator's instructions. The investigator will instruct all subjects to maintain stable dosing of medication for at least two weeks prior to scheduled follow-up visits.

#### **B.6.20. Device Explant**

At any time during the study, a subject with an implanted SCS device system may elect to withdraw from the study and have the SCS device system explanted. Additionally, an Investigator may elect to explant the device due to an adverse event.

The Investigator must follow the appropriate guidelines set forth by the manufacturer (i.e. Medtronic) for returning the explanted device and/or lead(s) as well as the accessories (charger, patient remote control).

#### **B.6.21. Early Subject Withdrawal**

Although efforts will be made by Investigators and study staff to encourage subjects to remain enrolled in the study, subjects may withdraw early from the study for a number of reasons, including but not limited to:

- Failure of SCS Trial Phase
- Subject request
- Investigator request
- Subject lost to follow-up
- Subject's death
- Adverse events (e.g., intolerable adverse event occurrence that forces subject to stop participation in the study)

If a subject is considering withdrawing from the study due to unsatisfactory effectiveness of the assigned treatment, the Investigator will make attempts to improve therapy during a study visit. When a subject is withdrawn early from the study, a Study Termination eCRF will be completed describing the reason for discontinuation. Study staff will contact subjects to remind them about their scheduled visits and make sufficient efforts to locate a subject that is not responding to a contact call. If a subject has withdrawn consent for the study, or is lost to follow-up, the completion of this visit is not required. In situations where study withdrawal is due to an adverse event, subjects will be followed until resolution of the adverse event or determination that the adverse event is not likely to change.

